3. TRIAL DESIGN

3.1 Overview of the clinical trial design

This is a Phase 3, open-label, international, randomized study to evaluate the efficacy and safety of ^{177}Lu -PSMA-617 in patients with progressive PSMA-positive mCRPC, when administered in addition to best supportive/best standard of care as compared to best supportive/best standard of care alone (Figure 1).

[figure not shown]

Figure 1 Diagram of trial design

ECOG = Eastern Cooperative Oncology group; EQ-5D-5L = European Quality of Life (EuroQol) – 5 Domain 5 Level scale; FACT-P = Functional Assessment of Cancer Therapy – Prostate; mCRPC = metastatic castration-resistant prostate cancer; PSMA+ = prostate-specific membrane antigen positive; RECIST = Response Evaluation Criteria in Solid Tumors

Best supportive/best standard of care includes available care for the eligible patient according to best institutional practice and at the discretion of the investigator. Novel androgen axis drugs [NAADs] (i.e., enzalutamide or abiraterone) are allowed.

Investigational agents, cytotoxic chemotherapy, immunotherapy, other systemic radio isotopes (e.g. radium-223) or hemi-body radiotherapy treatment may not be administered on study.

At screening, potential subjects will be assessed for eligibility and will undergo a ⁶⁸Ga-PSMA-11 PET/computed tomography (CT) scan to evaluate PSMA positivity. Only patients with PSMA-positive cancer will be randomized in a 2:1 ratio to receive either ¹⁷⁷Lu-PSMA-617 plus best supportive/best standard of care (investigational arm) or to receive best supportive/best standard of care alone (BS/BSC-only arm). Randomization will be stratified by 4 factors (Section 3.4.3).

Patients randomized to the investigational arm must begin ¹⁷⁷Lu-PSMA-617 dosing within 28 days after randomization. These patients will receive best supportive/best standard of care and 7.4 GBq ($\pm 10\%$) ¹⁷⁷Lu-PSMA-617 once every 6 weeks (± 1 week) for a maximum of 6 cycles.

After the Cycle 4 dose of ¹⁷⁷Lu-PSMA and prior to Cycle 5 Day 1, the investigator should determine if:

- The patient shows evidence of response (i.e. radiological, PSA, clinical benefit) and
- Has signs of residual disease on CT with contrast/MRI or bone scan and
- Has shown good tolerance to the ¹⁷⁷Lu-PSMA-617 treatment.

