3.4.3 Subject allocation to treatment

Patients will be randomized by an interactive response system in a 2:1 ratio to the investigational treatment arm (¹⁷⁷Lu-PSMA-617 plus best supportive/best standard of care) or the best supportive/best standard of care-only arm using a permuted block scheme. Randomization will be stratified by the following factors:

- LDH (\leq 260 IU/L vs. $>$ 260 IU/L)
- Presence of liver metastases (yes vs. no)
- ECOG score (0 or 1 vs. 2)
- Inclusion of NAAD in best supportive/best standard of care at time of randomization (yes vs no)

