AE = adverse event; ANC = absolute neutrophil count; BPI-SF Brief Pain Inventory – Short Form; CBC = complete blood count; CT = computed tomography; ECOG = Eastern Cooperative Oncology Group; EQ-5D-5L = European Quality of Life (EuroQol) – 5 Domain 5 Level scale; FACT-P = Functional Assessment of Cancer Therapy – Prostate; MRI = magnetic resonance imaging; PSA = prostate-specific antigen; PSMA = prostate-specific membrane antigen; WBC = white blood cell

Table 5 Schedule of assessments: Best supportive/best standard of care only arm (Cycle 1)

Study Period:	Cycle 1					
	Week 1	Week 2	Week 3	Week 4	Week 5	Week 6
Cycle Week:	Day 1	Day 8	Day 15	Day 22	Day 29	Day 36
Concomitant medication review	X-----					X
AE monitoring ^b	X-----					X
Weight	X ^a					
ECOG	X ^a					
Directed physical exam	X ^a					
Vital signs ^c	X ^a					
EQ-5D-5L	X ^{d,f}					
FACT-P	X ^{d,f}					
BPI-SF	X ^{d,f}					
Best supportive/ best standard of care	As per physician's orders					
Hematology ^e	X ^a	X ^a	X ^a	X ^a	X ^a	X ^a
Chemistry ^e	X ^a	X ^a	X ^a	X ^a	X ^a	X ^a
Serum/plasma testosterone	X ^a					
PSA	X ^a					
Radiographic imaging (CT with contrast/MRI and bone scan)	Every 8 weeks (\pm 4 days) after Cycle 1 Day 1 ^g for the first 24 weeks (independent of dose delays), then every 12 weeks (\pm 4 days) through the End of Treatment visit					

^a Can be done up to 3 days prior to Day 1. For hematology and chemistry: up to 3 days prior to Days 1, 8, 15, 22, 29, and 36.

^b Adverse event monitoring will commence at time of consent.

^c Blood pressure, pulse and respiratory rate will be assessed at required physical exams (up to 3 days of Day 1).

^d To be completed prior to any drug administration (if applicable) on Day 1. Can be completed up to 3 days prior to Day 1.

^e Hematology and chemistry to be done every week for Cycle 1 only.

^f HRQoL and pain assessments may be self-completed by subject or administered in interview format and completed by a caretaker, clinician or site research team member.

^g Cycle 1 Day 1 for patients on the Best supportive/best standard of care only arm is considered as the day that the majority of the day 1 assessments are conducted

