5.4 Subgroup Definitions

The following subgroups are defined for the study:

1. Stratification Factor (based on CRF data) – Inclusion of NAADs (e.g., enzalutamide, abiraterone, or apalutamide) as part of assigned BSC/BSoC treatment at start of study (Yes vs. No). See Section 5.6 for derivation.
2. Number of cycles in the ¹⁷⁷Lu-PSMA-617 + BSC/BSoC treatment arm (≤ 4 cycles vs. 5-6 cycles).
3. Stratification factor (based on CRF data) – Baseline LDH (≤ 260 IU/L vs. > 260 IU/L). See Section 5.6 for derivation.
4. Stratification factor (based on CRF data) – Presence of liver metastases at baseline (Yes vs. No). See Section 5.6 for derivation.
5. Stratification factor (based on CRF data) – ECOG score at baseline (0 or 1 vs. 2). See section for derivation.
6. Age (< 65 years vs. ≥ 65 years)
7. Race (White vs. Black or African American vs. Asian vs. Other (includes “Native Hawaiian or Other Pacific Islander”, “American Indian or Alaska Native” or more than one race reported))

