5.4.1 Analyses on subgroups

All subgroup analyses are to be considered exploratory and descriptive; p-values presented with efficacy results will be treated as nominal.

Efficacy analyses The alternate primary endpoints, rPFS and OS, will be summarized and analyzed by the following subgroups (defined in Section 5.4) to assess the consistency of treatment effect provided either or both primary endpoints are statistically significant:

- Inclusion of NAADs as part of assigned BSC/BSoC treatment at start of study
- Baseline LDH
- Presence of liver metastases at baseline
- ECOG score at baseline
- Age
- Race

No formal statistical test of hypotheses will be performed for the subgroups. For each subgroup, a stratified cox regression model will be used to estimate the treatment effect

stratifying for the randomization factors from IRT. When one of the stratification factors is the subgroup of interest, that factor will be excluded from the stratified model. The model will include three terms: treatment, subgroup (e.g. ECOG score at baseline) and treatment by subgroup interaction. The HR and associated confidence interval for each subgroup will be estimated from the model. Kaplan-Meier estimates as described for the alternate primary endpoints (Section 8.2.1) will also be provided excluding the log-rank test p-value. Subgroup analyses of rPFS and OS will be presented graphically using forest plots.

The efficacy analyses in subgroups will only be performed if at least 10% of patients or 10 patients are present in each class.

Key safety analyses of exposure, adverse events and clinical laboratory values will be performed as described in Section 9, on the FAS and PSMA-11 safety analysis sets (defined in Section 5.3.2) in the following subgroups (defined in Section 5.4):

- Inclusion of NAADs as part of assigned BSC/BSoC treatment at start of study (FAS Safety Analysis Set only)
- Number of cycles received in the ¹⁷⁷Lu-PSMA-617 + BSC/BSoC treatment arm (FAS Safety Analysis Set only)
- ECOG score at baseline (FAS Safety Analysis Set only)
- Age (FAS Safety Analysis Set and PSMA-11 Safety Analysis Set)
- Race (FAS Safety Analysis Set and PSMA-11 Safety Analysis Set)

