Stratification factor (based on CRF data) – Baseline LDH (≤ 260 IU/L vs. > 260 IU/L) is defined as the latest LDH value on or before the date of randomization as collected on the laboratory CRF page.

Stratification factor (based on CRF data) - Presence of liver metastases at baseline (Yes vs. No) is defined as at least one target and/or non-target liver lesion on or before the date of randomization and/or within 28 days of start of randomized treatment as captured on either the target or non-target lesion CRF pages.

Stratification factor (based on CRF data) – ECOG score at baseline (0 or 1 vs. 2) is defined as the ECOG score captured on the Enrollment CRF page.

Stratification Factor (based on CRF data) – Inclusion of NAADs (e.g., enzalutamide, abiraterone, or apalutamide) as part of assigned BSC/BSoC treatment at start of study (Yes vs. No) is defined as having a NAAD indicated as study BSC/BSoC (see Section 5) on or before the date of C1D1.

6. Study Patients

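### The CRF-based NAAD subgroup for rPFS and OS is closed at C1D1, after open-label allocation, so membership can depend on the arm

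*SAP*

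**What the plan says.** Protocol 3.4.3 stratifies randomization by "Inclusion of NAAD in best supportive/best standard of care at time of randomization (yes vs no"), and SAP 3.2 repeats the factor. The Protocol has BSC/BSoC chosen before randomization (section 3.1; Table 2 in section 6.1).

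For subgroups the SAP uses CRF data instead. SAP 5.4 lists NAAD inclusion "as part of assigned BSC/BSoC treatment at start of study (Yes vs. No). See Section 5.6 for derivation". SAP 5.6 then says that the factor "is defined as having a NAAD indicated as study BSC/BSoC (see Section 5) on or before the date of C1D1". The words that matter are "on or before the date of C1D1". In SAP 5.4.1, "The alternate primary endpoints, rPFS and OS, will be summarized and analyzed by the following subgroups", and the list includes "Inclusion of NAADs as part of assigned BSC/BSoC treatment at start of study". The model there has treatment, subgroup and their interaction. It is stratified by the IRT factors, except that the factor under study is dropped.

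On timing, Protocol 3.1 requires investigational-arm patients to begin "dosing within 28 days after randomization". For the control arm, a footnote in Protocol Appendix 1 says that C1D1 "is considered as the day that the majority of the day 1 assessments are conducted". I found no limit on the interval from randomization for that arm.

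The study is open-label (SAP 3.2). NAADs are allowed and BSC/BSoC may be changed over time (Protocol 5.2). SAP 5 identifies study BSC/BSoC drugs from a pre-specified list applied to concomitant medications and sets the CRF's own BSC/BSoC flag aside.

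**The concern.** A baseline subgroup should be settled before the arm is known. This one closes later. A physician or patient who learns of a control allocation may add a NAAD before C1D1, and the SAP variable cannot tell that NAAD from one planned at screening. If additions differ by arm and go with prognosis, the patients compared within Yes and within No are no longer the groups that randomization balanced. The forest plots could then show a treatment-by-NAAD difference that does not exist, or hide one that does.

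NAAD inclusion is a stratification factor, so readers are likely to take its row as a comparison within randomized strata. The same variable enters the IRT-CRF discordance table (SAP 6.4), which presents the CRF value as the true stratum. There, a start after randomization is indistinguishable from an IRT entry error.

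**Working it through.** **Comparing the definitions**

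| Item | Source | Cut-off |
|---|---|---|
| NAAD factor for randomization | Protocol 3.4.3, SAP 3.2 | Care plan at randomization |
| CRF LDH factor | SAP 5.6 | Last value by the randomization date |
| Efficacy baseline in general | SAP 5 | Randomization date (28-day imaging allowance) |
| CRF NAAD factor | SAP 5.6 | C1D1 |

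The NAAD cut-off departs from the factor that it stands for and from the SAP's general efficacy baseline rule. With open-label allocation, modifiable BSC/BSoC and the drug-list rule, membership can depend on the arm. The SAP also does not say how randomized patients who never reach C1D1 are classified, although the FAS and PFS-FAS keep them and early dropout was mainly in the control arm (SAP 3.1, 5.3.1).

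**Counts under an assumed rate**

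The plan has no figure to reproduce here. Suppose that 10% of control and 2% of investigational patients move from No to Yes between randomization and C1D1 (assumption).

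- OS, FAS: 814 split 2:1 is 543 and 271. Movers: 0.10 × 271 ≈ 27 control; 0.02 × 543 ≈ 11 investigational.
- rPFS, PFS-FAS: 557 split 2:1 is about 371 and 186. Movers: 0.10 × 186 ≈ 19 control; 0.02 × 371 ≈ 7 investigational.

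**Effect on the hazard ratios**

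I simulated 400,000 patients per scenario. The inputs are assumptions, although the HR and control median match the plan's rPFS design values: 2:1 allocation, HR 0.67 in everyone with no interaction, control median 4 months, and 50% with a NAAD at randomization. An unmeasured prognostic factor with HR 2 is present in half the patients. Only control patients without a NAAD add one, and one prognostic group does so four times as often as the other.

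| Control No patients adding | Who adds more | HR Yes | HR No | Ratio Yes/No |
|---|---|---|---|---|
| 10% | good prognosis | 0.696 | 0.670 | 1.04 |
| 20% | good prognosis | 0.712 | 0.651 | 1.09 |
| 30% | good prognosis | 0.718 | 0.625 | 1.15 |
| 10% | poor prognosis | 0.675 | 0.700 | 0.96 |
| 20% | poor prognosis | 0.662 | 0.719 | 0.92 |
| 30% | poor prognosis | 0.651 | 0.740 | 0.88 |

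With membership fixed at randomization, both subgroups stay at 0.68 to 0.69. That is slightly above 0.67 because the prognostic factor is left out of the model. With half the controls already on a NAAD, the 10% of all controls used in the counts corresponds to the 20% rows.

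**Comparison with sampling error**

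The variance of a log HR is about 1/(events × 2/9) under 2:1 allocation. Assume that events split evenly between Yes and No.

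- OS: 508/2 = 254 deaths per subgroup. SE = √(1/(254 × 2/9)) = 0.133. The 95% CI around 0.67 is 0.67 × exp(±1.96 × 0.133), or 0.52 to 0.87.
- rPFS: 364/2 = 182 events per subgroup. SE = √(1/(182 × 2/9)) = 0.157. The CI is 0.49 to 0.91.
- The Yes/No ratio has SE √2 × 0.133 = 0.188 for OS, so chance alone spans a factor of exp(1.96 × 0.188) = 1.45 either way. The largest simulated distortion is 1.15.

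**The case against.** The strongest defence is that C1D1 is a sensible proxy for the plan. The factor is inclusion in planned care, which is decided before randomization, and SAP 5 dates the first BSC/BSoC administration at C1D1. A NAAD planned at screening may properly start only then, and cutting start dates at randomization would call that patient No. This stands, and it rules out that repair. It does not rescue the definition, because a NAAD added after allocation passes the same test.

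The SAP also offers partial safeguards. Section 6.4 summarises IRT and CRF strata by arm and cross-tabulates their discordance. Section 9.1 summarises NAAD receipt by arm, and section 9.7 lists medication dates. Much of the migration could be reconstructed from these outputs. They expose the mismatch, but the forest-plot row keeps the C1D1 definition.

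Three stronger readings are tempting and are not supported:

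- **That the primary results are biased.** SAP 8.2 uses IRT strata for efficacy analyses. Subgroup results are exploratory with nominal p-values and are produced only if a primary endpoint succeeds (SAP 5.4.1).
- **That control patients have a 28-day window.** That limit is stated only for first dosing in the investigational arm. The control interval is not stated.
- **That a material false interaction is to be expected.** The documents give no rate of NAAD additions, by arm or overall. The simulated distortions need selective additions in one arm and still lie within sampling error.

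**Conclusion.** The point holds as a minor flaw of definition. The variable behind the NAAD subgroup for rPFS and OS closes after open-label allocation and can take in NAADs added because of the arm. This follows from the text alone. The size cannot be estimated from the documents. At plausible rates it is probably small, with hazard ratios shifted by a few hundredths in either direction, but that judgement rests on the assumed prevalence, prognostic factor and pattern of additions above. What is affected is the exploratory NAAD subgroup estimates and the reading of the discordance table. The primary tests, power and type I error are not affected.

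**What to change.** In SAP 5.4 and 5.4.1, define the NAAD subgroup for the rPFS and OS analyses and forest plots by the IRT stratum. It is recorded at randomization, exists for every randomized patient including those who never reach C1D1, and already stratifies the primary tests. Keep the C1D1-based CRF version as a sensitivity analysis. Add a table, by arm, of NAADs started between randomization and C1D1, so that discordance in SAP 6.4 can be separated into later starts and entry errors.

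Do not replace C1D1 with the randomization date as a cut on start dates, since that would misclassify NAADs planned beforehand and started at C1D1.

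The cost is SAP wording and one table; no data collection or treatment rule changes. The small downside is that IRT entry errors carry into the main subgroup rows; the CRF sensitivity version shows their effect.

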6.1 Patient Disposition

Sample size flow will be displayed in a consort diagram, and the following patient data will be summarized in tables.

Patient disposition for all patients who signed an informed consent:

- Number of patients who signed informed consent
- Number of patients screened
- Number of patients who were screen failures and the reason for screen failure
- Number of patients administered ⁶⁸Ga-PSMA-11 (PSMA-11 Safety Analysis Set)

By treatment arm and combined:

- Number of randomized patients – Full Analysis Set
- Number of randomized patients on or after March 5, 2019 – PFS Analysis Set
 - Number (%) of patients in Response Evaluable Analysis Set
- Number of randomized patients administered study treatment (FAS Safety Analysis Set)

Enrollment by country and center will be summarized for all screened patients and also by treatment arm using the FAS.

End of treatment status and the end of study status for all patients in the FAS, PFS-FAS and in the FAS randomized prior to 5 March 2019 will be summarized, by treatment arm and combined:

- Number (%) of patients treated, not treated and still on treatment
- Number (%) of patients discontinued from ¹⁷⁷Lu-PSMA-617 and BSC/BSoC, separately and all study treatments
- Number (%) for each primary reason for discontinuation from ¹⁷⁷Lu-PSMA-617 and BSC/BSoC, separately
 - Number (%) for reason for withdrawal of consent for ¹⁷⁷Lu-PSMA-617 and BSC/BSoC, separately
 - Time to withdraw consent (in days) continuous and categorical (1, 2-28, 29-56, >56)
- Number (%) of patients continuing in long-term follow-up period (i.e. patients who agreed to long-term follow-up and have not discontinued from the study)
- Number (%) of patients discontinued from study
- Number (%) for each primary reason for discontinuation from study
 - Number (%) for reason for withdrawal of consent for ¹⁷⁷Lu-PSMA-617 and BSC/BSoC, separately
 - Time to withdraw consent (in days) continuous and categorical (1, 2-28, 29-56, >56)

6.1.1 Sub-study

Patient disposition for all patients who signed an informed consent in the sub-study will be summarized and will include the following: Number of patients who signed informed consent, Number of patients screened, Number of patients who were screen failures and the reason for screen failure, Number of patients administered ⁶⁸Ga-PSMA-11 (PSMA-11 Sub-study Analysis Set), Number of patients administered ¹⁷⁷Lu-PSMA-617 and BSC/BSoC (Sub-study Safety Analysis Set). End of treatment and end of study status will also be summarized as described above for all patients in the Sub-study Safety Analysis Set.

6.2 Protocol Deviations

For the FAS, major protocol deviations will be summarized for each treatment arm and overall. The details of all deviations (major and minor) will also be listed by treatment and patient ID. All Protocol deviations (major and minor) will be recorded as part of the Trial Master File (TMF).

Specific protocol deviation categories will be assigned to important deviations related to COVID-19 (e.g. missing efficacy assessments and treatment interruptions) and these will be summarized separately and flagged in the listings.

6.2.1 Sub-study

A listing of all deviations (major and minor) will be listed for the Sub-study Safety Analysis Set. Specific protocol deviations related to COVID-19 will be flagged in the listing.

6.3 Inclusion and Exclusion Criteria

For all screened patients, a summary of all inclusion criteria not met and exclusion criteria met will be provided. An additional summary will be provided for the PSMA-11 Safety Analysis Set. A listing, including the protocol version the patient was consented under and a flag for the FAS population, will be provided for all screened patients.

6.3.1 Sub-study

A listing of all inclusion criteria not met and exclusion criteria met will be provided for all screened patients in the sub-study.

6.4 Stratification Information

For the FAS, PFS-FAS and the Response Evaluable Analysis Set, the number (%) of patients in each randomization stratum based on data obtained from the IRT system and data collected on the CRF (see Section 5.6) will be summarized by treatment arm and overall. The randomization stratification factors are: LDH (≤ 260 IU/L vs. > 260 IU/L); presence of liver metastases (yes vs. no); ECOG score (0 or 1 vs. 2); and inclusion of NAAD in best supportive/standard of care (yes vs no) at time of randomization. Discordance between the stratum recorded in the IRT system and the actual stratum through data collected in the CRF will be cross-tabulated for the FAS, PFS-FAS and Response Evaluable Analysis Set and listed for the FAS.

7. Baseline Characteristics and Prior and Concurrent Therapies and Medications

All tables in Section 7 will be presented by treatment arm and for all patients combined for the FAS, PFS-FAS, the Response Evaluable Analysis Set, FAS Safety Analysis Set and the PSMA-11 Safety Analysis Set (defined in Section 5.3) unless otherwise specified. For tables using the PSMA-11 Safety Analysis Set, an additional column will be included for patients not enrolled (i.e. not randomized).

7.1 Demographic and baseline assessments

Descriptive statistics of patient characteristics at baseline will be presented for the following:

- Age (years): continuous and categorical (<65 vs. ≥ 65 , <65 vs. $\geq 65-84$ vs. ≥ 85)
- Race (White vs. Black or African American vs. Asian vs. Others (includes "Native Hawaiian or Other Pacific Islander, American Indian or Alaska Native")

- Ethnicity
- Height (cm)
- Weight (kg)
- BMI (kg/m²)
- ECOG performance status (0 or 1 vs. 2) Note: ECOG performance status is captured on the Enrollment CRF page and not collected at the time of screening. Thus, ECOG performance status will not be available for those not enrolled.

7.2 Baseline Disease Characteristics

Descriptive statistics of patient disease characteristics at baseline will be presented for the following variables:

- Time since initial prostate cancer diagnosis (years)
- Initial Histopathological Classification
- Initial Histopathological Grade
- Initial Gleason score
 - Categorical: 2-3,4-7,8-10, unknown
- Stage at Initial Diagnosis
- Total Sum of Target Lesions Diameters per RECIST 1.1
- Baseline Target Lesions (Yes vs. No) and Non-Target Lesions (Yes vs. No)
- Site of disease (lung (yes/no), liver (yes/no), lymph node (yes/no), bone (yes/no), other (yes/no) using target and non-target lesions or bone scan assessments (bone only); sponsor to provide categorization)
- Baseline PSA doubling time (months): continuous and categorical (≤ 6 vs. >6)
- Baseline PSA
- Baseline ALP
- Baseline LDH

Note: The baseline variables 'Total Sum of Target Lesions Diameters', 'Target Lesions and Non-Target Lesions' will be based on the data collected on target/non-target lesion assessment according to RECIST 1.1 according to local investigator assessment and documented in the CRF. 'Site of disease' will be based on the data collected on either the target/non-target lesion assessment (per RECIST 1.1) or the bone scan assessment per local investigator assessment and documented in the CRF.

